MEL-T01 and MEL-S01 have negligible risks to the subject. They are non-invasive cognitive-training-software devices that the subject engages with at home. Pre-clinical evaluation based on internal testing and a pilot study showed no serious adverse effects on the previous version of the game. Adverse effects reported from the population sample of N = 54 were frustration (16.7%) that was almost invariably caused by device deficiencies, i.e., by problems in the technical implementation of the game, boredom due to limited content (14.8%) and anxiety from gameplay pressure (1.8%). Technical implementation of the game has been greatly improved since the previous version hence it is less likely that this kind of adverse effects are reported due to technical problems. More content has been developed into the game.

The version 1.0 made 14.1.2022 has received an approval from the HUS ethical committee (HUS/3043/2021).

Table 1: The overview of the study

Study arms	T0 (Before playing)		T1: T0 + 4 weeks		T2: T0 + 8 weeks		T3: T0 + 12 weeks		T4: T0 + 24 weeks
MEL-T01 intervention		MEL-T01 intervention						Follow-up	
MEL-S01 intervention		MEL-S01 intervention						Follow-up	
Treatment as usual ("TAU")		Treatment as usual						MEL-T01 or MEL-S01 intervention	

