3.3.1.1 Adverse events (AEs) in earlier game-based interventions and DTx trials

In our pre-clinical feasibility study in 2019 with a sample of $N = 54$ MDD patients, no serious adverse events (SAEs) were reported. The three most common adverse event (AEs) were

1. frustration (AE reported by 16.7% of subjects)
2. boredom (14.8%)
3. Stress (1.8%)

Frustration was almost invariably caused by objective device deficiencies, i.e., problems in the technical implementation of the game. Boredom was attributed to limited unlockable content (progression levels) in this game version. Stress was defined to arise from the time pressure in the game.

Since this pre-clinical study, we have made considerable improvements to the game and to the investigational device framework. The game has gone through several rounds of testing and quality assurance, which has led to the elimination of all so far discovered device deficiencies

and greatly improved usability and user experience. We believe this effort will lead to significantly lower amounts of frustration AEs in the MelioraRCT trial.

We have also added considerably more content, expanding the prior 14 progression levels into 28, which makes it possible for the subject to enjoy new game elements for well over 25 hours of game time. We believe that this will limit the occurrence of boredom AE.

Finally, time-pressure is an integral part in the design of the investigational device for achieving its therapeutic efficacy. We have improved the device's user interface and communication about the device's goals to mitigate the stress as an AE.

In a previous RCT study on a game-like software-based digital therapeutics for ADHD, Kollins et al. (2020) report that of their 180 subjects 12 had intervention-related adverse events, 5 experienced frustration, 3 headache, 2 had emotional reactions, 1 dizziness, 1 had nausea, 1 had aggression. There were no serious adverse events or discontinuations due to the AEs. Overall, the subjects had exclusively mild treatment-related adverse events.

MEL-T01 and MEL-S01 closely resemble commercially freely-available entertainment video games that are considered safe and widely used as entertainment. In Finland 78% of people play digital games, and, on average, people play 7 hours per week (Kinnunen et al., 2020).

However, as all activities, video gaming also has risks, even if they are mild. These are considered below.

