3.3.1.2 Anticipated AEs

In guidelines for good clinical practice E6(R2) European medicines agency defines adverse events (AE) as: *“Any untoward medical occurrence in a patient or clinical investigation subject administered a pharmaceutical product and which does not necessarily have a causal relationship with this treatment.”*

The subjects may have unanticipated or anticipated adverse events during the study. Below, we have identified anticipated AE that may arise in the use of the MEL-T01 or MEL-S01 software. The list is based on possible negative events that may occur from playing entertainment video games (see Playstation, 2022) that closely resemble the MEL-T01 and MEL-S01 software. The adverse events are:

- Frustration
- Boredom
- Stress
- Eye ache
- Headache
- Dizziness
- Nausea
- Neck pain

- Visual disturbances
- Migraine
- Muscle twitching
- Uncomfortable feelings or ache in hands
- Losing sense of time and space

We take measures to mitigate the anticipated AE. We guide the user to pay attention to ergonomics, ensure sufficient lighting, and keep breaks while playing. Should the user encounter any AE, they are guided to stop playing, and report the AE to the researchers either through the in-game link or email. The information to the subjects is included in Appendix 2 (Tutkittavan tiedote) and the information given to the subject is found in Appendix 6 (Investigator's brochure). For AE reporting procedures, see [3.14](#).

Another risk is the potential addiction that video games may create. To mitigate this risk, we take the following precautions: 1) Digital game addiction is an exclusion criteria for the study. 2) We only recommend playing 45 minutes per day, and the players cannot play the game for more than 90 minutes per day at which point the game locks them out. 3) Our game doesn't include highly addictive features such as so-called loot boxes.

"A very small percentage of individuals may experience epileptic seizures or blackouts when exposed to certain light patterns or flashing lights." (Playstation, 2022). Considering the risk for epileptic seizure, we exclude subjects who have a history of epilepsy from the study to mitigate the risk. We also inform the subject about this (see Appendix 6 - Investigators brochure, 2.2.5.).

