3.5 Objectives and hypotheses of the clinical investigation

Main objective

The primary objective of this research is to assess the effectiveness of MEL-T01 in reducing MDD symptoms. The subjects are randomised into three research arms (MEL-T01, MEL-S01, and TAU), and their subject health questionnaire (PHQ-9) scores are measured on five occasions (see Table 1).

Research arms

- MEL-T01
- MEL-S01
- TAU

Time intervals

- T0, before subjects in MEL-T01 and MEL-S01 arm begin the active intervention.
- T1, 4 weeks after T0
- T2, 8 weeks after T0

- T3, 12 weeks after T0
- T4, 24 weeks after T0

Primary hypotheses

- MEL-T01 is superior to TAU in alleviating MDD symptoms as measured by the change in subject health questionnaire (PHQ-9) score between time points T0 (before the intervention) and T3 (after a 12-week intervention).
- MEL-S01 is superior to TAU in alleviating MDD symptoms as measured by the change in PHQ-9 score between T0 and T3.
- MEL-T01 superior to MEL-S01 as measured by the change in PHQ-9 score between T0 and T3.

Secondary hypotheses

- In terms of a score change from T0 to T3,
MEL-T01 is superior to TAU,
and MEL-S01 is superior to TAU,
and MEL-T01 superior to MEL-S01 in:
 - reducing depression symptoms as measured by quick inventory of depressive symptomatology (QIDS),
 - reducing rumination as measured by short-version ruminative response scale (RRS),
 - reducing anxiety symptoms as measured by general anxiety disorder (GAD-7),
 - reducing the disability symptoms as measured by sheehan disability scale (SDS),
 - increasing positive emotions as measured by positive valence systems scale (PVSS),
 - and
 - improving well-being as measured by the WHO-five well-being index (WHO-5)
- The effect of the MEL-T01 is mediated by the training dose, as measured by the subject's total game-playing time during the intervention, and evidenced by a positive correlation between MEL-T01 game time and reduction in symptoms as measured by the PHQ-9.
- The effect of the MEL-S01 is mediated by the training dose, as measured by the subject's total game-playing time during the intervention, and evidenced by a positive correlation between MEL-S01 game time and reduction in symptoms as measured by the PHQ-9.

- The effects of MEL-T01 on depressive symptoms as measured by PHQ-9 are mediated by positive game experience as measured by the immersive experiences questionnaire (IEQ).

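### Anxiety harm would be collected as adverse events but not systematically compared between arms: GAD-7 is analysed only as mean change for improvement, without device users who stop before 24 hours, and one pilot event carries two names

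*Combined protocol and SAP*

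**What the plan says.** **Pilot event.** The synopsis (3.1.6, safety assessments) reads "Adverse effects reported from the population sample of N = 54 were frustration (16.7"%), followed by boredom at 14.8% and "anxiety from gameplay pressure (1.8"%). Section 3.3.1.1 describes the same study: "In our pre-clinical feasibility study in 2019 with a sample of $N = 54$ MDD patients, no serious adverse events (SAEs) were reported". It gives the same figures for frustration and boredom, and then stress at 1.8%, with the explanation "Stress was defined to arise from the time pressure in the game". It adds that "time-pressure is an integral part in the design of the investigational device for achieving its therapeutic efficacy".

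**Adverse event list and definition.** Stress is on the anticipated list in 3.3.1.2 and in Table 2 (3.3.1.6). The word anxiety is in neither. Section 3.3.1.2 quotes a general definition, "Any untoward medical occurrence in a patient or clinical investigation subject administered a pharmaceutical product", and guides a subject who has an adverse event to stop playing and report it. Section 3.3.1.3 asks subjects to report every adverse event, anticipated or not. Section 3.14.1 gives four reporting channels, with recording, weekly review, and grading of causality and severity.

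**GAD-7.** It is collected at T0 to T4 (3.7.1.2, Table 5). Its hypothesis in 3.5 is superiority in "reducing anxiety symptoms as measured by general anxiety disorder (GAD-7"). Game addiction (GAS), by contrast, has an exploratory hypothesis about an increase. Section 3.7.2 requires at least 24 hours of play for the primary analysis and treats the secondary hypotheses in the same way. Under 3.6.4.3 the clinical subject coordinators (CSCs) see suicidality-related replies but no other questionnaire replies.

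**The concern.** The plan ties an anxiety or stress event to time pressure, a feature kept by design, and 3.6.1 notes that anxiety is common in depressed patients. It holds a repeated anxiety score for every arm, yet uses it only to ask whether mean anxiety falls further on one arm than on another.

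Three features weaken that comparison as a check on harm:

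- A mean can fall while some subjects worsen.
- A device user who becomes anxious, stops playing as guided and has not reached 24 hours leaves the comparison. TAU subjects have no device during those 12 weeks, so this route out exists only in the device arms.
- Spontaneous reporting is not a symmetric substitute. The in-game channels are closed to TAU subjects before T3, and the coordinators cannot prompt on a rising GAD-7 score.

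At stake is whether the synopsis statement that risks are negligible gets checked for anxiety with data the trial already collects.

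**Working it through.** **1. Is it the same pilot event?** Inputs are from 3.1.6 and 3.3.1.1, N = 54 in both.

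| Event | Stated | Count/54 | Result |
|---|---|---|---|
| Frustration | 16.7% in both | 9/54 | 16.67% |
| Boredom | 14.8% in both | 8/54 | 14.81% |
| Anxiety (3.1.6) or stress (3.3.1.1) | 1.8% in both | 1/54 | 1.85%, printed truncated |

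Sample, companion figures and cause (pressure in the game) agree. The two sections describe one subject under two names.

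**2. How much does one event tell us?** The exact (Clopper-Pearson) 95% interval for 1/54 is 0.05% to 9.9%. Subjects randomised to a device: 800 × 2/3 = 533. Expected events: 533 × 1.85% = 9.9, with limits 533 × 0.047% = 0.25 and 533 × 9.89% = 53.

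**3. Who is left in the GAD-7 comparison?** Section 3.7.4.1 plans 133 per arm. An exact two-sided t calculation with d = 0.40, alpha 0.0167 and power 0.80 reproduces 133 (power 0.803), and 400/0.50 = 800. In the two device arms that means 2 × 133 = 266 analysed of 533, so about 267 lie outside the comparison for all reasons together. The plan does not say how many of these would stop because of an adverse event, or how many would still return a GAD-7.

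**4. What would the planned test show if mean anxiety rose?** The sidedness of the GAD-7 test is not stated. Section 3.7.3 fixes a one-tailed test for PHQ-9 only and writes the general alternative as two-sided. No GAD-7 effect size is given, so the values of d below are assumed (0.40 is borrowed from PHQ-9), with 133 per arm and alpha 0.0167.

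| True rise (d) | Two-sided test detects it | One-sided test for improvement |
|---|---|---|
| 0.40 | 0.80 | below 0.000001 |
| 0.30 | 0.52 | below 0.0001 |
| 0.20 | 0.22 | below 0.0001 |

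**5. Can a mean hide worsening?** Assume 10% of an arm rise by 1 SD and 90% fall by 0.2 SD. The mean change is 0.10 × 1 − 0.90 × 0.2 = −0.08 SD, an apparent improvement. This shows only that it is possible.

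**6. What could a count of worseners detect?** Two-proportion test, two-sided 0.05, all rates assumed.

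| Device vs control | n per arm | Power |
|---|---|---|
| 10% vs 3% | 133 | 64% |
| 10% vs 3% | 266 | 91% |
| 17% vs 10% | 266 | 66% |
| 27% vs 20% | 266 | 48% |
| 4.85% vs 3% (excess equal to the pilot rate) | 266 | 19% |

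Power depends heavily on the background rate, which the documents do not give. The table is therefore best treated as descriptive.

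**The case against.** The strongest reply is that anxiety is not overlooked. A reader might infer that a device-caused rise in anxiety would go unreported; the documents do not support that. The pilot event is on the anticipated list and in Table 2 as stress. If anxiety counts as something else, it is an unanticipated event, which 3.3.1.3 and 3.14.1 still collect, record and grade. Mean GAD-7 change is compared for all three arm pairs, no text makes that test one-sided, and 3.6.1 speaks of influencing anxiety in either direction. A rise in the mean would be visible in the estimates.

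A reader might also infer that the quoted definition bars adverse events in TAU from serving as a background rate. Read literally, its reference to a pharmaceutical product would exclude the software arms as well, so it does not single out TAU. Coordinator calls and email are not limited to the device arms, and 3.3.1.3 says an event may or may not be device-related.

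Nor does the earlier game-based trial show that the list is deficient. It reported "2 had emotional reactions, 1 dizziness, 1 had nausea, 1 had aggression", but in a paediatric ADHD population.

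All of this stands. It does not answer the selective loss of early stoppers, the absence of any worsening summary, or the unequal reporting channels. Section 3.14.1 mentions scheduled calls at weeks 0, 4, 8, 12 and 24, which would help, but 3.7.1.2 and 3.10.1 describe calls only when a questionnaire is late. The information for subjects in Appendices 2 and 6 was not available for this review.

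**Conclusion.** The point holds and is minor. One pilot event (1/54, exact 95% CI 0.05% to 9.9%) has two names that need reconciling. Anxiety events would be collected, but the plan has no systematic between-arm comparison of anxiety harm, and the comparison it does have can lose device users who stop early because of an adverse event.

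The size of that loss cannot be computed from the documents. The upper bound is the roughly 267 of 533 device-arm subjects expected to fall outside the analysis for any reason. The conclusion rests on two readings: that treating secondary hypotheses similarly in 3.7.2 carries the 24-hour rule over to GAD-7, and that Table 6 means TAU subjects have no in-game access before T3. It does not rest on the assumed rates in the power illustrations.

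**What to change.** 1. Reconcile 3.1.6, 3.3.1.1, 3.3.1.2 and Table 2 against the pilot record, so that the event has one name throughout.
2. In 3.7.3 add a descriptive safety table in all randomised subjects with any post-T0 GAD-7, regardless of play time. By arm, give the distribution of GAD-7 change at T1, T2 and T3, and the number whose score rises from T0 by at least a threshold fixed before unblinding. Give two-sided confidence intervals for each arm pair.
3. In the same section state whether the GAD-7 efficacy test is one- or two-sided.
4. In 3.3.1.2 state that adverse events are recorded in all arms from T0, whether or not related to the device, since the quoted definition fits no arm of this trial.

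The cost is a few lines of text and one table from data already collected. Subjects who return no questionnaire after T0 will still be missing, so their number should be shown by arm. The table has limited power for small excesses, and the absence of a difference should not be read as evidence of safety.

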3.3.1.2 Anticipated AEs

In guidelines for good clinical practice E6(R2) European medicines agency defines adverse events (AE) as: *“Any untoward medical occurrence in a patient or clinical investigation subject administered a pharmaceutical product and which does not necessarily have a causal relationship with this treatment.”*

The subjects may have unanticipated or anticipated adverse events during the study. Below, we have identified anticipated AE that may arise in the use of the MEL-T01 or MEL-S01 software. The list is based on possible negative events that may occur from playing entertainment video games (see Playstation, 2022) that closely resemble the MEL-T01 and MEL-S01 software. The adverse events are:

- Frustration
- Boredom
- Stress
- Eye ache
- Headache
- Dizziness
- Nausea
- Neck pain

- Visual disturbances
- Migraine
- Muscle twitching
- Uncomfortable feelings or ache in hands
- Losing sense of time and space

We take measures to mitigate the anticipated AE. We guide the user to pay attention to ergonomics, ensure sufficient lighting, and keep breaks while playing. Should the user encounter any AE, they are guided to stop playing, and report the AE to the researchers either through the in-game link or email. The information to the subjects is included in Appendix 2 (Tutkittavan tiedote) and the information given to the subject is found in Appendix 6 (Investigator's brochure). For AE reporting procedures, see [3.14](#).

Another risk is the potential addiction that video games may create. To mitigate this risk, we take the following precautions: 1) Digital game addiction is an exclusion criteria for the study. 2) We only recommend playing 45 minutes per day, and the players cannot play the game for more than 90 minutes per day at which point the game locks them out. 3) Our game doesn't include highly addictive features such as so-called loot boxes.

"A very small percentage of individuals may experience epileptic seizures or blackouts when exposed to certain light patterns or flashing lights." (Playstation, 2022). Considering the risk for epileptic seizure, we exclude subjects who have a history of epilepsy from the study to mitigate the risk. We also inform the subject about this (see Appendix 6 - Investigators brochure, 2.2.5.).

3.3.1.3 Unanticipated AEs

Besides anticipated AE, it is possible that the subject encounters unanticipated AE. The subject is encouraged to report all AE, whether unanticipated or anticipated, to the researchers. Subjects' channels for reporting AE are covered in [3.14](#).

The anticipated or unanticipated AE may or may not be related to the device use which the coordinating investigator assesses case-by-case, see [3.14](#).

3.3.1.4 Serious adverse events (SAEs)

According to the European Medicines Agency, SAE includes death, threat to life, requires hospitalisation or prolongation of existing hospitalisation, results in persistent or significant disability/incapacity, or is a congenital anomaly or birth defect.

As MEL-T01 and MEL-S01 are software and essentially indistinguishable from many commercially available entertainment video games, the risk for serious adverse effects is very low.

Should SAE occur during the study, the coordinating investigator evaluates all SAE cases for their possible connection with MEL-T01 or MEL-S01, as described in [3.14](#).

3.3.1.5 Eliminated risks

Eliminated risks include risks that are possible regarding digital video games but which we have eliminated through the device design.

Social conflicts. Many video game softwares have interaction between players which may lead to negative side-effects such as social conflicts and bullying. To negate this risk, MEL-T01 is a single-player game. This means that the player doesn't have any contact with other players which negates the social risk.

Monetary losses. Some entertainment video games today have the potential to make additional purchases within the game which are called microtransactions. This may cause players to use more money on video games than they intended, which may lead to regret and even actual financial challenges. To negate the risk, our game is free to the player and the players cannot make real or virtual purchases in the game.

3.3.1.6 Summary of risks

Overall, we consider that MEL-T01 and MEL-S01 have low risks for the subject: the existing risks are of low impact and many of them are mitigated in the device design. The software is non-invasive, the subject uses it voluntarily with informed consent, and the subject can at any point quit the intervention. The device is similar to many entertainment video games, yet it doesn't include highly addictive features or allow social interaction between players that exist in some video games.

Overall, we consider that the benefits of MEL-T01 and MEL-S01 considerably outweigh the possible risks which we have mitigated. The game offers the player a meaningful experience in their everyday life through engaging, adaptive gameplay, and evolving, hope-inspiring narrative. The game offers the players a chance to relax while simultaneously challenging them. Should our video game prove effective in reducing the symptoms of depression, it may possibly have considerable social benefits. In this case, video games could offer a scalable, supplementary treatment option alongside the existing modes of treatment.

Please find a supplementary ethical consideration in: *Appendix 11 - Ethics Evaluation of the Study*, for a summary of the AE and SAE see [3.3](#), and regarding AE and SAE reporting see [3.14](#).

Table 2: Risk assessment table (see also [3.14](#))

Risk	Likelihood Before mitigation	Likelihood After mitigation	Severity of harm	Mitigation measures
Frustration Boredom Stress Physical AEs: Eye ache Headache Dizziness Nausea Neck pain Visual disturbances Migraine Muscle twitching Uncomfortable feelings or ache in hands Losing sense of time and space	Possible	Possible	Mild	Physical AEs: Health information about safe device usage and prevention of adverse events is available in-game continuously. The subject can stop playing anytime. See 3.14.
Epileptic seizure	Possible	Rare	Severe	History of epilepsy or seizures is an exclusion criteria for the study.
Game addiction	Probable	Possible	Moderate	Playing time is restricted Exclusion of addicted players No highly addictive game features No social interaction in the game No gambling elements in the game

3.3.2 Peripheral risk considerations

The following include other risks that we have considered in the design as well as those that have limited applicability to software devices but are named in REGULATION (EU) 2017/745.

